- A sequential explanatory mixed methods design will be used to evaluate the implementation process to determine mechanisms by which pay-it-forward motivates testing and donations across the two intervention arms, and how individual and organizational characteristics moderate these individual and organizational characteristics moderate these.
- This study will answer compelling scientific questions about how best to implement pay-it-forward and the individual and organizational characteristics that moderate it.

Background

Gonorrhea is common among MSM in China. Gonorrhea is one of the most common sexually transmitted diseases (STDs) worldwide and in China. The World Health Organization estimated 87 million new cases of gonorrhea among people 15-49 years old based on a 2016 global systematic review⁵. The prevalence of gonorrhea among MSM in southern China has been reported as high as 12.5%⁶⁻⁷. Gonorrhea is known to increase the risk of HIV acquisition and transmission but is often asymptomatic at extragenital sites.

Gonorrhea testing rates among MSM are low. World Health Organization⁹ and United States Centers for Disease Control and Prevention guidelines¹⁰ recommend routine gonorrhea testing for sexually active MSM. Studies in different provinces of China consistently report that less than half of MSM have ever been tested for gonorrhea¹¹⁻¹². Low testing rates are problematic because this allows onward gonorrhea transmission.

Low testing rates are likely related to fees and minimal community engagement. User fees are common in many low and middle-income countries for STD testing and discourage test uptake¹², decreasing opportunities for prompt treatment and public health interventions^{11,13}. Gonorrhea testing in China is expensive, not covered by health insurance, and not covered by other social support systems. This decreases access to routine gonorrhea testing¹⁴. Some young MSM may opt to self-pay for STD services in order to decrease the risk of parents, insurance providers, or others knowing about their need for services¹⁵. In addition to financing problems, community engagement in STD testing is often weak. Many MSM campaigns for STD testing are driven by public health authorities and have limited authentic input from local end-users¹⁶. This limited participation may then diminish STD test uptake. In response to these financial and community barriers to STD testing, our team developed a pay-it-forward approach to gonorrhea testing for MSM.

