The inclusion criteria at MSM-led clinics include men who had anal sex with another man; are at least 18 years old; have had anal sex over the past year; have not been tested for gonorrhea and chlamydia in the past year; reside in the city in the past three months; speak Mandarin Chinese or Cantonese; mentally capable of providing informed consent to test for gonorrhea and chlamydia; and owning a mobile phone. In China, over 95% of MSM own a mobile phone.

Development of intervention and formative research

Approach and study team

A key innovation of this trial study, relative to past pay-it-forward research, is developing and evaluating the community-engaged approach as an additional intervention arm. While upstream reciprocity is hypothesized to promote the pay-it-forward mechanism in our proposed trial, simulation models of the upstream reciprocity process show that the "warm glow" does not guarantee sustainability. In contrast, evidence shows that the probability of cooperation increases when combined with network reciprocity where a community of collaborators reinforces acts of altruism.⁷² The two arms of our trial are designed to test these two hypotheses. The standard pay-it-forward arm evaluates the hypothesis that the upstream reciprocity created by a pay-it-forward approach will increase testing adoption with minimal implementation support, while the community-engaged arm tests the hypothesis that pay-it-forward needs to be reinforced by an implementation strategy based on network reciprocity to enhance its effectiveness.

The study will be managed through a consortium involving two academic centers, the University of North Carolina in Chapel Hill and the Southern Medical University Dermatology Hospital in Guangzhou, as well as a non-profit community-based organization that will

organize community engagement activities, the Social Entrepreneurship to Spur Health (SESH). The SESH team has a strong track record of community engagement and organizing research studies focused on sexual health, including pay-it-forward programs in Beijing and Guangzhou. The study team comprises representatives from the academic centers and SESH who have complementary expertise in community mobilization, implementation science, epidemiology, health economics, biostatistics, and social science.

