A co-creation group will be appointed and will comprise MSM representatives, clinicians and nurses, communication officers, and co-chaired by members of SESH and a local MSM community-based organization. Co-creation groups serve as a source of shared leadership in CBPR-premised research, and its members typically reflect the community of interest. This co-creation group will be consulted on a quarterly basis to provide input on the study design, implementation, and dissemination activities.

Site selection, training, and trial registration

We will implement the study in Guangdong cities with MSM-led clinics: Huizhou, Zhuhai, Jiangmen, Foshan, Zhanjiang, and Dongguan. These clinics were chosen because respective cities have a higher burden of STDs, they include the two major service delivery approaches (MSM-led clinics and public clinics) in China, and findings would be potentially relevant in many cities that have chlamydia/gonorrhea point-of-care testing available.

Each of the clinical sites will receive Good Clinical Practice (GCP) training for new personnel, regulatory assessment, and related trial requirements. Representatives from each of the participating clinics will be invited to attend a single training workshop in Guangzhou to introduce the study protocol, local implementation workflows, sample collection and testing, gonorrhea and chlamydia treatment, and the resistance testing processes. We registered the RCT on ClinicalTrials.gov (registration id: NCT05723263) prior to the commencement of the trial.

Developing standard strategy and the community-engaged strategy

This three-arm cluster randomized controlled trial will compare gonorrhea test uptake in a standard pay-it-forward implementation strategy arm, a community-engaged pay-it-forward implementation strategy arm, and a control arm. Our implementation strategies are summarized in Table 1.

Table 1. Overview of the three study arms.

Trial Arm	Financial Component of Gonorrhea Testing*	Community Engagement
Standard Pay-it-forward arm	Free gonorrhea/ chlamydia testing	Passive: viewing postcards and materials written by others encouraging gonorrhea/ chlamydia testing Active: an opportunity

		to donate to support others.

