Community-engaged Pay-it-forward arm	Free gonorrhea/ chlamydia testing	Active: multi-stakeholder co-creation activities to develop essential components of the intervention and implementation strategies; writing postcards; designing fans with stickers,; sending out testing promotion messages on social media; an opportunity to donate to support others.
Control arm	Fee-based gonorrhea/ chlamydia testing (approximately 20 USD)	None

*Note: All participants who test positive for gonorrhea will receive a referral for AMR testing and treatment at the local public STD clinic.

In the standard strategy/arm, MSM who enter the clinic will be provided with a free gonorrhea test alongside handwritten postcards from other MSM in the local community. Our previous RCT has already created standard operating procedures, survey instruments, and educational materials for this intervention. The initial postcards were generated through an open call for suggestions about tailored, handwritten messages that are clinic-specific and locally appropriate. We used the standardized methods developed by the World Health Organization to design the open call. Briefly, this will involve creating a steering committee, promoting the open call, judging submissions, recognizing excellent submissions, and implementing selected ideas.

In contrast, the community-engaged strategy/arm will include all elements of the standard strategy, in addition to the following key components: gift recipients will be invited to select a handwritten postcard for keepsakes, submit handwritten postcards of their own, draw on and decorate plain hand fans with stickers, send out messages promoting gonorrhea/chlamydia testing on social media platforms, or create videos promoting gonorrhea testing (to be viewed at the same clinic). Men who agree to participate in the community-engagement activities will be invited to a pay-it-forward event where they will meet other people who have donated, and will also be invited to related participatory activities organized by the local clinic to promote gonorrhea testing.

In the control arm, MSM will be informed about the importance of gonorrhea testing but will not receive handwritten postcards or other community engagement activities. Among men who choose to receive gonorrhea testing, they will have access to the same diagnostics,

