and qualitative data separately) and the results were interpreted together. Generalized mixed-effects models will be used to examine two main hypotheses: one comparing the superiority of the community-engaged strategy compared to the standard pay-it-forward strategy; and another comparing the superiority of the standard pay-it-forward strategy to the control arm. The estimated intervention effects will be reported with 95% C.I.s and p-values. Descriptive analysis will be used to summarize the characteristics and behaviors of the participants in each arm.

Implementation evaluation

The RE-AIM framework has been extensively used in implementation research to evaluate the implementation of evidence-based interventions. At this stage, we will evaluate the other dimensions of the implementation of the standard pay-it-forward and the community-engaged pay-it-forward arms with a view to understand both the factors that influence men to get tested and those that motivate men to donate. Given the novelty of pay-it-forward to raise funds, its sustainability partly depends on men willing to donate. Understanding the drivers of financial sustainability across individuals and clinics may help inform policymakers and interested researchers in resource-limited settings about the potential of using the strategy to promote underfunded public health services.

We will use a sequential explanatory mixed methods design.⁹³ In this design, quantitative data is followed up with qualitative methods to expand or explain the quantitative results. The quantitative component of our design will measure reach, implementation, adoption and maintenance by adapting validated implementation research instruments to assess acceptability and appropriateness at the individual level (related to adoption) and fidelity and organizational readiness at the clinic level (related to implementation). Details of these instruments are provided in Table 3 below. The qualitative data will use in-depth interviews grounded in upstream and social reciprocity theories to explore the processes and mechanisms that affect the results, and how these differ by individual (geography and socioeconomic) and organizational (geography and readiness) characteristics. Our mixed methods study will be conducted during and after the RCT.

Quantitative surveys

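### No randomized contrast in the trial isolates upstream reciprocity: standard pay-it-forward and control also differ in price, postcards and the donation opportunity

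*Combined protocol and SAP*

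**What the plan says.** The section Development of intervention and formative research, under Approach and study team, sets out two mechanism hypotheses and states: "The two arms of our trial are designed to test these two hypotheses". The first is assigned as follows: "The standard pay-it-forward arm evaluates the hypothesis that the upstream reciprocity created by a pay-it-forward approach will increase testing adoption". The sentence goes on to specify minimal implementation support, and gives the community-engaged arm a different hypothesis, reinforcement through network reciprocity.

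Data analysis, in the section on the pragmatic cluster RCT, names two main hypotheses. One is superiority of community-engaged over standard pay-it-forward; the other is "another comparing the superiority of the standard pay-it-forward strategy to the control arm".

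Table 1 gives the financial component of both pay-it-forward arms as "Free gonorrhea/ chlamydia testing" and that of the control arm as "Fee-based gonorrhea/ chlamydia testing (approximately 20 USD". The standard arm also has postcards and materials written by others and an opportunity to donate. The text after Table 1 says that control men "will not receive handwritten postcards or other community engagement activities".

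On price, the Background says: "User fees are common in many low and middle-income countries for STD testing and discourage test uptake". It also describes gonorrhea testing in China as expensive and uninsured.

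**The concern.** The protocol attributes a mechanism to a design feature. The theory section explains it: a gift produces a positive feeling and a sense of obligation, which leads a man to be tested and to give. To test this by randomization, two arms would have to differ in the gift relationship and in nothing else that moves uptake. Here the gift and the removal of the fee are the same act, and the protocol itself names fees as a cause of low testing.

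What is at stake is interpretation. Under the present wording, superiority of standard over control could be read as confirming upstream reciprocity when a plain free test might have produced some or all of it. The Implementation evaluation section hopes to inform policymakers in resource-limited settings. Some of them may have plain free testing as their alternative, and this trial does not study that option.

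**Working it through.** **1. What differs between the arms** (Table 1 and the arm descriptions that follow it)

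| Element | Control | Standard | Community-engaged |
|---|---|---|---|
| Price | about 20 USD | free | free |
| Peer postcards and messages | no | yes | yes |
| Opportunity to donate | no | yes | yes |
| Co-creation, writing postcards, fans, social media, videos, events | no | no | yes |

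**2. What each contrast estimates.** Write F for the effect of removing the fee, R for the effect of the gift framing with postcards and donation opportunity, I for any interaction, and E for the effect of the added engagement activities.

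- Standard − control = F + R + I
- Community-engaged − standard = E

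The first is one equation in at least two unknowns. No arm gives a free test without the pay-it-forward elements (F alone), and none gives those elements at the usual fee (R alone). The second contrast holds price constant, but the gift, postcards and donation opportunity are in both arms, so R cancels. Neither contrast yields R, and upstream reciprocity is at most part of R.

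**3. Whether another analysis fills the gap.** Table 2 compares the gratitude, solidarity and cohesion scales by t-test. A difference between arms in gratitude would not show that gratitude caused testing, and no mediation analysis is specified. The interviews can describe motives but do not estimate an effect net of price.

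**4. The plan's own figure.** 3 arms × 4 clinics × 100 men = 1200, as stated. The stated 90% power cannot be reproduced, because the plan gives no uptake rates, target difference or ICC.

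**5. Illustration on assumed values.** Suppose R = I = 0, so that price is the whole effect. Control uptake (20%), the price effect d and the ICC are assumptions, not figures from the documents. Alpha is 0.05, taken as two-sided.

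- Effective n per arm: n = 400 / (1 + 99 × ICC), which is 201.0, 134.2, 67.2 and 36.7 for ICC 0.01, 0.02, 0.05 and 0.10.
- Normal approximation: power = Φ{[d − 1.96 √(2p̄(1 − p̄)/n)] / √[(p1(1 − p1) + p2(1 − p2))/n]}, with p̄ the mean of p1 and p2.
- Example, ICC 0.02, 20% against 40%: [0.20 − 1.96 × √(0.42/134.2)] / √(0.40/134.2) = (0.20 − 0.110)/0.0546 = 1.65, so power is 95%.
- Small-sample version: noncentral t with 2 × (4 − 1) = 6 df.

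Chance of a significant standard-against-control result (normal / t with 6 df):

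| ICC | d = 10 points | d = 20 points | d = 30 points |
|---|---|---|---|
| 0.01 | 64% / 50% | 99% / 96% | ~100% / ~100% |
| 0.02 | 47% / 36% | 95% / 86% | ~100% / 99% |
| 0.05 | 27% / 21% | 72% / 58% | 96% / 89% |
| 0.10 | 16% / 13% | 46% / 36% | 78% / 66% |

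The clinic is taken as the independent unit, as in the sample-size section. Allocating both clinics of a city together, as the abstract says, would tend to lower these chances. The table shows only that a significant result is possible, and under some inputs likely, with no reciprocity effect at all.

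**The case against.** The strongest reply is that the confirmatory analysis makes no mechanism claim. Objective 1 compares test uptake between strategies, and Data analysis tests one strategy against control. Both are package comparisons. The price difference is declared in Table 1 and in the design overview. Under the protocol's theory the free test is the gift, so it belongs to the intervention. Mechanism is assigned separately to objective 2, with its scales and interviews. The sentence under Approach and study team can be read as the rationale for having two pay-it-forward arms, and it does not name the control arm as comparator.

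Most of this stands. The hypothesis in Data analysis needs no substantive change, and comparing a whole programme with fee-based testing is a legitimate pragmatic question. What remains is that the protocol says outright that the arms are designed to test the mechanism, and standard against control is the only planned contrast that could carry that hypothesis. Making the free test part of the intervention does not help, because a free test can raise uptake without any sense of reciprocity.

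A reader might also infer that the effect would be expected from fee removal alone. The documents do not support that: the Background gives a direction for fees but no size. Nor can a range be put on the fee's share. If the donation request deterred some men, the fee effect could exceed the whole observed difference.

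**Conclusion.** The point holds as a matter of interpretation. The trial cannot test whether upstream reciprocity increases testing, although the protocol says that its arms are designed to do so. This follows from the description of the arms and depends on no assumed figure. The size of any misattribution cannot be estimated from the documents.

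Two stronger readings should be resisted. A reader might infer that the primary comparison is invalid. It is not: standard against control remains a valid randomized test of the package as a whole, and the test statistic, type I error and data collection are unaffected. A reader might also infer that community-engaged against standard can carry the reciprocity claim because both arms are free. It cannot: the gift is present in both, and the contrast is itself a bundle of engagement activities.

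**What to change.** Reword the hypothesis paragraph under Approach and study team to state three things:

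1. Standard pay-it-forward against control estimates the joint effect of free testing, peer messages and the donation opportunity compared with fee-based testing. Superiority will not be interpreted as evidence for upstream reciprocity over fee removal.
2. Community-engaged against standard, free in both arms, estimates the added effect of the bundled community-engagement activities and does not test upstream reciprocity.
3. Evidence on reciprocity comes from the gratitude and solidarity scales and the interviews under objective 2, and is exploratory.

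The hypotheses in Data analysis can stay as they are. Asking control-arm men who decline whether the fee was the reason would describe a barrier but would not identify reciprocity, so it is no substitute for the rewording.

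The cost is a few sentences and a narrower, less favourable mechanistic conclusion. No arm, clinic, participant or analysis is added.

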Methods: PIONEER will be a three-arm, programmatic cluster randomized controlled trial (RCT) to compare the effectiveness of the three implementation strategies, followed by a mixed-methods implementation evaluation study guided by a transformative paradigm. For the cluster RCT, we will enroll 12 diverse clinics, which will be randomly assigned to one of the intervention arms for delivering gonorrhea testing: a standard pay-it-forward implementation strategy with minimal encouragement to get tested, a community-engaged pay-it-forward strategy, and a control arm in which men pay for their own STD test. The public and MSM-led clinics in the same city will be randomized to the same study group to prevent contamination. The primary outcome of the RCT will be gonorrhea test uptake, and secondary outcomes will include chlamydia testing, STD treatment among those with infection, amount donated, 100% condom use, and antimicrobial resistance. A sequential explanatory mixed methods design will be used to evaluate the implementation process. Data sources will include survey data on the acceptability of the intervention, intervention appropriateness, feelings and attitudes towards the interventions among participants, administrative data about test uptake, treatment rate, and donations, as well as qualitative data to gain insights about men's perceptions and attitudes towards the pay-it-forward interventions strategies, mechanisms driving uptake and donating behaviors. Both survey and qualitative interviews with implementers and organizers about fidelity and adherence to protocol, intention to continue and maintain a pay-it-forward intervention, and barriers and facilitators of implementing the intervention will be conducted.

Discussion: PIONEER will substantially increase gonorrhea testing among MSM in China, providing an innovative new financial mechanism to sustain STD screening among sexual minorities in low- and middle-income countries. This study will answer compelling scientific questions about how best to implement pay-it-forward and the individual and organizational characteristics that moderate it.

Contributions to the literature

- This cluster randomized controlled trial aims to examine the effectiveness of two implementation strategies involving different levels of community engagement to translate the generosity created by the pay-it-forward approach into test-taking action.

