We have developed an interview guide as part of formative testing. The main topics in the interview guide will include the following: (1) reasons for getting tested; (2) understanding and perception of the pay-it-forward concept; (3) specific questions about emotions of gratitude after receiving a test that is supported by another community member; and (4) self-identity in the MSM community and level of integration within a community; (5) intention and motivation to initiating and mediating helping behaviors within the community. We will obtain recorded verbal informed consent from all interviewees before the commencement of the interview. Interviews will last about one hour and will take place either in person or over the phone-based on participant preference.

Interviews will be audio-recorded, and personal information will not be recorded. Unintentional recording of personal information will otherwise be redacted before transcription. Each participant will receive a small monetary incentive of ¥50 (7.50 USD) for their participation. All recorded interviews will be transcribed, and the transcripts will be checked by one research staff member. Summaries of interviews will be written up for preliminary data analysis. In addition, we will collect anonymized text from handwritten postcards and other community engagement activities.

Pragmatic cluster RCT

Sample size and power considerations

We used a binary outcome cluster RCT design for sample size calculation where the unit of randomization is the clinic. In order to achieve a 90% power and allow for 0.05 type-I error, 12 overall clusters (4 in each arm) are needed. Thus, the sample size includes a total of 12 clusters and 1200 participants (100 per cluster) based on cluster randomized trial sample size calculation principles. We expect this study will have 85% power to detect a 10% difference in azithromycin resistance between intervention arms and routine gonorrhea antibiotic surveillance data from other cities in the same province. Nevertheless, further calculations will be made following formative research endeavors that will estimate the prevalence of these outcomes. The calculation would be performed using the software PASS (version 15) with the formulas developed by Hussey and colleagues.³⁶

Randomization

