Figure 2 shows the cluster RCT design flowchart. We will assign clinics to study arms on a 1:1:1 basis using covariate-constrained randomization. We will use covariate-constrained randomization to decrease potential bias associated with unbalanced study arms. We will balance the number of MSM-led and public clinics in each arm because these are unique implementation structures. All men recruited via one clinic will be assigned to one arm. We will recruit and screen men until we meet our sample size of 1200 men.

[figure not shown]

Figure 2. Pragmatic RCT flowchart. Each city will have one MSM-led clinic and one public clinic participating.

Intervention delivery strategies

The duration of the intervention is one year at each clinic, with the potential to continue based on local commitments. All patients who accept testing will receive gonorrhea/chlamydia PCR testing. This diagnostic is approved by the US FDA and the Chinese national regulatory authority. Men who agree to be tested will have specimens collected from

pharyngeal, rectal, and urethral sites. Specimens will be pooled based on excellent sensitivity and specificity. Turnaround time for test results will depend on the local clinic. Surveys will be done online in order to facilitate implementation. All participants diagnosed with gonorrhea will receive ceftriaxone and azithromycin in accordance with WHO recommendations for first-line gonorrhea therapy.

Outcome measures

The primary outcome of the RCT will be gonorrhea test uptake ascertained by administrative review from participating clinics. We used this same primary outcome in previous quasi-experimental and RCT trials evaluating pay-it-forward. Secondary outcomes will include syphilis testing, amount donated towards pay-it-forward, antimicrobial resistance measures, positive tests for gonorrhea and chlamydia, measures of gratitude and community solidarity, and per unit costs associated with the intervention (Table 2).

Table 2. Secondary outcomes of the cluster RCT			
Outcome	Time Frame	Ascertainment	Data Analysis
Primary			
Gonorrhoea and Chlamydia test uptake		Clinic administrative data	Generalized mixed effects models (compare control arm to pay-it-forward intervention)
Secondary			
Amount donated	During enrollment visit	Administrative data	Descriptive analysis
The number of participants who tested positive for Gonorrhea	During enrollment visit	Laboratory result	Descriptive analysis

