The number of participants tested positive for chlamydia	During enrollment visit	Laboratory result	Descriptive analysis
The proportion of those who tested positive for Gonorrhea or Chlamydia who returned for referral treatment	One month after receiving the results	Self-reported follow-up survey (linkage to care, treatment)	Descriptive analysis
Cost per test ¹	During enrollment visit	Costing data collection	Micro-costing approach

Adapted gratitude scale	During enrollment visit	Self-report	T-test
Community solidarity scale ⁴	During enrollment visit	Self-report ²	T-test
Community cohesion	During enrollment visit	Self-report	T-test
Internalized homophobia	During enrollment visit	Self-report	T-test
Subgroup analysis			
Gonorrhea and chlamydia testing uptake by clinic type	During enrollment visit	Administrative data at study site	MSM-led clinic vs. public STD clinic
Gonorrhea and chlamydia testing uptake by sexual orientation	During enrollment visit	Self-reported sexual orientation data from baseline survey	Self-identified sexual minority vs. not
Gonorrhea and chlamydia testing uptake by age group	During enrollment visit	Self-reported socio-demographic data from baseline survey	≤30years vs. >30years
Gonorrhea and chlamydia testing uptake by PrEP eligibility	During enrollment visit	Self-reported frequency of condom use in during sexual intercourse in the past 3 months data from baseline survey	Condom use vs. Condomless sex.

¹Cost per test is defined as the cost associated with respective interventions (development, start-up, implementation, intervention) per individual who reported testing for gonorrhea and chlamydia following the intervention; economic test and financial cost are reported separately.
 
²Community solidarity involves engagement, social network support, and a sense of belonging. These items were used in our previous pay-it-forward research study..
			

Data analysis

Data will be analyzed using a transformative mixed method research approach. The primary outcome will be gonorrhea and chlamydia test uptake among MSM. Quantitative and qualitative data will be analyzed using a convergent parallel design (i.e., analyze quantitative

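### The 90% power treats 12 clinics as independently randomized, but both clinics of a city share an arm; the best reading is 6 units (2 per arm), so the calculation does not support 90%

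*Combined protocol and SAP*

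**What the plan says.** **Power.** Under Pragmatic cluster RCT, Sample size and power considerations, the plan describes a "binary outcome cluster RCT design for sample size calculation where the unit of randomization is the clinic". It then states: "In order to achieve a 90% power and allow for 0.05 type-I error, 12 overall clusters (4 in each arm) are needed". Each cluster has 100 men, 1200 in all. For the primary outcome it gives no control uptake, effect, ICC or sidedness. It adds that "further calculations will be made following formative research endeavors that will estimate the prevalence of these outcomes".

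**Allocation.** The Methods paragraph of the abstract says: "The public and MSM-led clinics in the same city will be randomized to the same study group to prevent contamination". The Figure 2 caption says: "Each city will have one MSM-led clinic and one public clinic participating". Site selection, training, and trial registration names six cities.

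**Text that points elsewhere.** The Randomization section says: "We will assign clinics to study arms on a 1:1:1 basis using covariate-constrained randomization". Study setting and population allows cities that have only one of the two clinic types. Design overview bases randomization on city economic status and stratifies by clinic type.

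**Analysis.** Data analysis (cluster RCT) plans generalized mixed-effects models for two main hypotheses: community-engaged versus standard pay-it-forward, and standard versus control. It names no random-effect level.

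**The concern.** Power in a cluster trial depends on how many units are allocated independently. If two clinics always go to the same arm, whatever their city has in common does not average out between them, and they are not two independent allocations. A calculation for 12 separate clinics then understates the variance of the arm contrast whenever part of the between-clinic variance belongs to the city.

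The primary outcome and both main hypotheses are affected. The headline power would rest on twice as many randomized units as the design appears to have. Because the model's cluster level is not named either, nothing shows that the analysis would take account of the shared allocation.

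**Working it through.** **1. Number of randomized units.** Twelve clinics at one MSM-led and one public clinic per city make 12 / 2 = 6 cities, which matches the six named. Under the abstract's rule each city is one allocation: 6 / 3 = 2 per arm, with 2 x 100 = 200 men each. Balancing on city economic status is compatible with this, and balance of clinic type follows automatically from city pairs. The eight pay-it-forward clinics mentioned under Implementation evaluation (2 arms x 4) fit either reading and decide nothing.

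**2. The plan's own figure.** The 90% cannot be reproduced, because control uptake, effect and ICC are missing. What follows is therefore relative: fix the effect that gives exactly 90% with 12 independent clinics, then change only the allocation. *Assumptions:* two-sided 5%; clinic ICC (rho) 0.01-0.05; s = share of the between-clinic variance that lies at city level.

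**3. Variance of an arm mean,** in units of p(1-p):

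- 4 independent clinics: [rho + (1-rho)/100] / 4
- 2 cities of 2 clinics: rho·s/2 + rho·(1-s)/4 + (1-rho)/400
- Ratio R = 1 + s·rho / [rho + (1-rho)/100]

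Example, rho = 0.02 and s = 0.5: R = 1 + 0.5 x 0.02/0.0298 = 1.336.

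**4. Power with the reference distribution unchanged.** The noncentrality for 90% is 3.24 (normal). Power is Φ(3.24/√R − 1.96). For the example, 3.24/1.156 = 2.80 and Φ(0.84) = 80%.

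| rho | s = 0 | s = 0.10 | s = 0.25 | s = 0.5 (R) | s = 1 (R) |
|---|---|---|---|---|---|
| 0.01 | 90% | 89% | 86% | 83% (1.25) | 75% (1.50) |
| 0.02 | 90% | 88% | 85% | 80% (1.34) | 71% (1.67) |
| 0.05 | 90% | 88% | 84% | 78% (1.42) | 67% (1.84) |

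Planning and testing with t on 9 df (12 clinics − 3 arms; noncentrality 3.65) gives the same figures to within about half a point.

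**5. Adding a small-sample reference.** With t on 3 df (6 cities − 3 arms) and s = 0, 90% becomes 59%, 68.5% or 74% if the trial was planned with z, t on 9 df or t on 6 df (noncentrality 3.91). That part comes from the few units, not from shared allocation. With s from half to all, power is 38-51%, 46-60% and 50-65% respectively.

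**6. If 4 per arm was rounded up.** Suppose 90% was just met with 3 clinics per arm. The noncentrality at 4 is 3.24 x √(4/3) = 3.74, so planned power is Φ(1.78), about 96%. Shared allocation then gives 88-92% at s = 0.5 and 79-86% at s = 1 (normal reference).

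**7. Dependence on the effect.** For an assumed 20% versus 40% uptake, t on 9 df throughout: at rho = 0.01, 97.8% with 12 clinics becomes 94.5% (half) or 90.1% (all); at rho = 0.02, 90.2% becomes 80.5% or 71.4%.

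**8. What the unnamed analysis level could do.** I simulated 40,000 null trials per setting, with mean uptake 50% and s from half to all. If clinic were the only cluster level, type I error per contrast is about 8-20% with clinic type adjusted for. With type left out it is about 9-22% if the types do not differ, but 0.1-5% if they differ by 20 points. A city-level t test on 3 df stays close to 5% in these runs.

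**The case against.** **The unit is not certain.** The rule that ties a city's clinics together appears only in the abstract. The sample size and Randomization sections speak of assigning clinics, and one-clinic cities are allowed. This stands: six units is the best reading, not a fact. It does not rescue the calculation, because any city with two clinics under that rule leaves fewer than 12 independent allocations.

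**The calculation is provisional.** The later calculations are tied to outcome prevalence, not to the randomized unit, and none appears in Version 6.0.

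**True power may still be 90% or more.** This stands. A reader might infer that power is below 90% whichever reference distribution is used. The documents do not support that. They do not say whether 4 clusters per arm gave exactly 90% or was rounded up, and steps 6 and 7 show cases that remain at or above 90%.

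**The city share is assumed.** This also stands. At zero share nothing is lost through shared allocation. Balancing on city economic status might remove some city variance if it is also adjusted for in the analysis.

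**The error rates belong to an analysis nobody specified.** Correct. One might read step 8 as showing that the planned test is inflated, but the plan does not say that clinic is the only level, and the direction depends on clinic type. The Randomization section says "We will balance the number of MSM-led and public clinics in each arm because these are unique implementation structures", and Table 2 lists "Gonorrhea and chlamydia testing uptake by clinic type", so adjustment for type is plausible but not stated.

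**Conclusion.** The inconsistency is established from the text. Power was computed for 12 clinics as independent units, while the abstract's allocation rule, the Figure 2 caption and the list of cities point to 6. As written, the calculation does not support 90%.

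The direction of the error follows if any between-clinic variance lies at city level: power is lower than calculated. Its size does not follow from the documents. The figures in steps 4 to 7 are illustrations that rest on an assumed ICC, city share, effect and two-sided testing, and they do not show that true power is under 90%. The missing random-effect level is a real gap, but step 8 describes a hypothetical analysis.

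Confidence is high for the inconsistency and limited for the amount of power lost. The point should be corrected before analysis, since with perhaps two units per arm the choice of analysis unit can decide the result.

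**What to change.** 1. Reconcile the abstract, Design overview, Study setting and population, Sample size and power considerations, and Randomization. State the randomized unit, and the number of units per arm, once.
2. If the same-city rule stands, replace the 90% with power recomputed for the actual number of city units. Use a parallel-group cluster formula with small-sample critical values, and state the control uptake, effect, city and clinic ICC, and sidedness. (The reference-list entry that fits the named formula source concerns stepped-wedge trials.)
3. For both main hypotheses, base inference on the randomized unit, with clinic type as a fixed effect and a small-sample method. A city-level summary analysis, or a mixed model with city and nested clinic effects, would do. The exact degrees of freedom are for the trial statistician to choose.

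**Cost:** protocol and SAP wording and a rerun of the power calculation; no added sites or men. **Downside:** this restates power and does not restore it. The stated power becomes less favourable and the confidence intervals wider.
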